## **Supplemental Qualitative Interview: Those who participate in the supplemental qualitative**

**interview will receive additional \$30 compensation. The supplemental qualitative interview will take approximately 20-30 minutes to complete.**

## Biochemical Assessment of Smoking Status.

Consistent with most published smoking cessation RCTs (see Clinical Practice Guidelines), our

primary study outcome will be biochemically confirmed 7-day point prevalence abstinence 26 weeks following the scheduled quit date. Secondary outcomes (e.g., 30-day point prevalence, time to first lapse, longest time of quit) will also be examined. Smoking abstinence will be measured daily via EMA self-reports and the Bedfont iCO smokerlyzer will be used to verify smoking status on 3 days per week (during the end of day EMA). Participants will be prompted to connect the iCO device to the study smartphone and follow step-by-step directions to complete the iCO test (e.g., hold your breath countdown, exhale countdown; See Figure 8). Results of these tests will be date and time stamped and saved. The Smart-T algorithm will utilize the results of the iCO test to inform the feedback that is delivered at the completion of EMAs. Please note that we have integrated automated and secure (i.e., encrypted) facial recognition software to ensure that only the participant completes prompted iCO tests. Our CO criteria for abstinence is consistent with numerous studies using cutoffs of  $\leq 6$  ppm. The half-life of CO is up to 8 hours depending on a variety of factors (e.g., time of day, daily smoking rate, recency of smoking, physical activity). Studies have shown that expired CO is a valid indicator of smoking status and cessation outcomes and compares favorably with cotinine and other biochemical measures that have longer detection windows. We believe that self-reports of abstinence combined with CO levels suggestive of recent abstinence provide an accurate, immediate, and practical measure of abstinence. Finally, the manufacturer indicates that the iCO is valid for approximately 200 CO tests and has a sensor sensitivity of 1 ppm. Our protocol will require 81 CO testing sessions (3 per week for 27 weeks), allowing for repeated tests when/if needed.

## Description of Study Visits

The Baseline visit will take approximately 60-90 minutes to complete and data will be collected on laptop/tablet computers using Questionnaire Development System (QDS) software. Staff will be available to help participants who may have difficulty. The Remote Baseline process will occur via phone calls with research staff, and data will be collected via REDCap surveys. Up to 30 participants will complete a 16-week qualitative interview with a staff member over the phone regarding their experiences in the study so far.

The 26 week post-quit follow-up assessment is a longer than usual phone based EMA that will take 20-30 minutes to complete. Up to 100 intervention group participants and up to 100 control group participants will complete a 15-30 minute qualitative interview with a staff member over the phone (or via REDCap if a medical condition prevents them from being able to speak for long periods of time) as part of their 26 week post-quit follow-up assessment. Constructs that will be assessed are listed in Table 3 and actual assessment items are presented in Appendix A.

## E. Statistical Methods

**Aim 1.** We will compare the proportion of participants that are biochemically verified as abstinent (i.e., iCO and self-reports indicate no smoking in the past 7 days) between the treatment conditions (i.e., Smart-T vs. QuitGuide), at 26 weeks post-quit using a chi-square or

Fisher's exact test. We will perform the analysis under the intention to treat (ITT) assumption wherein participants who miss iCO EMAs will be considered not abstinent. We will examine the missing rate and missing patterns before analysis. If the combined missing rate is very small, say less than 5%, then we may safely perform the data analysis on the available data or the data assuming ITT. If the missing rate is high, then we will explore sequential multiple imputation (SMI) as described by Raghunathan et al. The analysis results from SMI data will be compared with those from the available data and ITT analyses. Based upon previous studies of mobile phone based interventions for smoking cessation (see Cochrane Review), we expect that 9% of those receiving the QuitGuide + NRT treatment will be abstinent at the 26 week post- quit follow- up visit, and based upon our pilot work, we expect that 18% of those receiving the Smart-T + NRT treatment will be abstinent at the 26 week post-quit follow-up visit (see). With an alpha of 0.05 and 225 participants in each group, we have 80% power to detect a 9% difference in biochemically confirmed 7-day point prevalence abstinence at 6 months (i.e., 18% abstinent in the Smart-T group vs. 9% abstinent in the QuitGuide group). We expect that groups will be similar in baseline characteristics (e.g., sex, nicotine dependence) due to randomization; however, in addition to the chi-square analysis, we will perform logistic regression to determine if the odds of abstinence vary by other baseline characteristics (e.g., sex, race/ethnicity). Finally, we will examine the interaction between treatment condition and sex (and race) to identify potential differential effects on abstinence. The enrollment/baseline type (e.g., in person vs. phone call) will be included as a potential covariate in analyses.

We will examine agreement across the iCO and self-reported abstinence measures. Also, we will use the self-report and iCO data to construct secondary outcome measures, including 30day point prevalence abstinence, time to first lapse, and longest period of abstinence, which will be compared between treatment conditions. Assuming an 80% iCO compliance rate for each participant, we anticipate 62 iCO measures per participant over the study. Lastly, we will examine changes in abstinence rates over time using generalized linear mixed model (GLMM) regression analysis employing a random intercept or slope parameter, as appropriate, and modeling the covariance structure for the repeated outcome measures, while accounting for participant characteristics, such as sex.

**Aim 2.** To determine the impact of treatment condition (i.e., Smart-T vs. QuitGuide) on key lapse risk factors (i.e., smoking urge, stress, cigarette availability, and cessation motivation), we will examine the effect of tailored messages on lapse risk factors using consecutive pairs of EMAs in which the first EMA in the pair results in a tailored message. These paired EMA scores will be used to identify whether the change in the lapse risk factor rating from the first to the second EMA in the pair differs depending on whether the participant receives a tailored message or not (i.e., Smart-T vs. QuitGuide). Assuming that each participant will receive a message targeting a particular risk factor at least once, then we have greater than 80% power to observe an effect size of 0.27 or larger in the mean of the change in the score for that risk factor in the Smart-T group compared with the QuitGuide group. In the Smart-T feasibility study, mean changes in raw scores for key lapse factors ranged from 0.19 to 0.56; all effect sizes were 0.27 or larger, therefore we have ample power to detect potentially clinically relevant changes. There will be up to four pairs of EMAs per day across weeks 2-14 of the study. Assuming an 80% EMA completion rate and 25% of EMA pairs being considered high risk (thus resulting in a message tailored to a specific high risk trigger), we estimate 73 high risk EMA pairs to examine per participant. Roughly 25% of EMA pairs should target each key lapse risk factor, resulting in 18 EMA pairs for each message type per participant. With 225 participants per group, that provides 4,050 EMA pairs per message type per group to include in the longitudinal analyses, resulting in ample power to identify the minimal effect size assumed to be clinically relevant. We will also examine the changes in key lapse risk factor scores

using linear mixed model (LMM) regression analyses employing a random intercept or slope parameter, as appropriate, and modeling the covariance structure for the repeated outcome measures, while accounting for baseline participant characteristics. Another analysis will look across all paired EMA scores within an individual and assign each individual a success percentage score based on the number of times their paired EMA scores decreased by at least one point on the Likert scale. For example in an individual that has 50 paired EMA scores for smoking urge, if 40 resulted in a decrease in urge, 5 resulted in no change, and 5 resulted in an increase in urge, the success percentage score would be 80% (40/50). Then we can compare the mean success percentage scores between treatment conditions using independent t-tests followed by regression analysis to account for baseline participant characteristics. Additional analyses will compare success percentage scores early versus late in the study to examine if the effectiveness of tailored messages change through time. Finally, we will examine the interaction between Smart-T message type and sex (and race) to identify potential differential effects on lapse risk factors.

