#### **A. Specific Aims**

The primary long-term objective of this research is to reduce smoking rates among low SES adults. The next step towards this goal is to use a fully powered randomized clinical trial to compare the efficacy of the Smart-T app with the free and widely available National Cancer Institute (NCI) QuitGuide app for smoking cessation in the 26 weeks following a scheduled quit attempt. A total of 450 socioeconomically disadvantaged, treatment-seeking males and females will be randomly assigned to receive either the Smart-T intervention app or the QuitGuide intervention app. All participants will receive nicotine replacement therapy and complete EMAs, but only the Smart-T group will receive intervention messages that are tailored to the current level of lapse risk and current lapse triggers. The study aims are to:

**1. Determine the impact of treatment condition (i.e., Smart-T vs. QuitGuide app; n=225 per group) on biochemically verified smoking abstinence.**

*Hypothesis 1:* Participants randomly assigned to Smart-T will have significantly higher rates of biochemically-verified abstinence than those assigned to QuitGuide at 26 weeks post-quit.

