
**Participant Flow.** Individuals who provide informed consent and meet the study inclusion criteria will complete the baseline assessment in TTRP clinic space (the TTRP is located in [name] in a building that is adjacent to the PI's office) or via phone calls with study staff.

Following the baseline assessment, participants will be given instruction on how to complete phone-based EMAs and carbon monoxide assessments. All participants, regardless of

condition, will be compensated for completing the baseline assessments, phone based follow-up, and EMAs. In addition, participants will complete expired breath carbon monoxide tests using the portable iCO device 3 days per week (weeks 1-27).

**Study Overview.** Eligible and interested individuals will be randomized to 1 of 2 groups: 1) Smart-T smoking cessation intervention plus NRT, or 2) NCI QuitGuide smoking cessation intervention plus NRT. Stratified randomization will be used to assign participants to groups based upon race, sex, and cigarettes smoked per day. Participants will be followed for 27 weeks and will attend either 1 in-person visit or complete phone-based baseline visits. Participants will be prompted to complete daily EMAs and tests of smoking status using a portable, low-cost, carbon monoxide monitor (Bedfont iCO Smokerlyzer) on 3 days each week. This data will be used to address primary (i.e., biochemically verified 7-day point prevalence abstinence at 26 weeks post-quit) and secondary outcomes (e.g., 30-day point prevalence abstinence, number of days to first lapse, longest period of smoking abstinence). Geographic location data will be captured multiple times per day to link characteristics of the present environment (e.g., proximity to tobacco outlets) with cessation-related outcomes. We have already created software that integrates the iCO sensor into our Insight™ mobile application platform.

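### The primary abstinence test ignores the three randomisation factors and leaves chi-square or Fisher's exact test open; the cost is a little power, not false positives

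*Combined protocol and SAP*

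**What the plan says.** Section D (Study Overview) sets the allocation: "Stratified randomization will be used to assign participants to groups based upon race, sex, and cigarettes smoked per day". It gives no race levels, cigarettes-per-day cut-points or block size.

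Section E, Aim 1, sets the primary analysis: "We will compare the proportion of participants that are biochemically verified as abstinent" "between the treatment conditions (i.e., Smart-T vs. QuitGuide), at 26 weeks post-quit using a chi-square or" Fisher's exact test. None of the three factors enters this comparison. A regression follows, but as a supplement: "in addition to the chi-square analysis, we will perform logistic regression to determine if the odds of abstinence vary by other baseline characteristics". Its examples are sex and race/ethnicity; cigarettes per day is not named anywhere in section E.

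The power statement reads "With an alpha of 0.05 and 225 participants in each group, we have 80% power to detect a 9% difference" (18% against 9%). It names no test, continuity correction or number of sides. Hypothesis 1 in section A is worded in one direction: Smart-T participants "will have significantly higher rates of biochemically-verified abstinence than those assigned to QuitGuide at 26 weeks post-quit".

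Under the intention-to-treat rule, "participants who miss iCO EMAs will be considered not abstinent". Elsewhere in section D, the paragraph on data loss prevention lets staff telephone participants whose EMA completion is low and allows those calls to be used as a covariate.

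**The concern.** Factors that govern the allocation normally belong in the primary analysis. If they predict quitting, stratified allocation balances them between arms, but an unstratified test still counts the variation they explain as noise. The test then rejects too rarely under the null and loses power under the alternative. The supplementary regression does not clearly fill the gap: it asks whether abstinence varies with baseline characteristics, is not described as the treatment test, and does not name the third factor.

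The second issue is that two tests are permitted and the power statement is tied to neither. By formula the design sits at 80% with nothing to spare, so a less powerful test falls below the stated figure.

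**Working it through.** **Inputs from the documents.** 225 per arm, 18% against 9%, alpha 0.05 (sections A and E). Missed iCO tests count as not abstinent, so all 225 per arm are analysed. Expected shares are 59% White, 25% Black, 10% American Indian, 6% other and 61% female (section F).

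**Reproducing the 80%.** Two-sided, pooled variance, no continuity correction:

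- Pooled rate = (0.18 + 0.09)/2 = 0.135
- SE under the null = √(2 × 0.135 × 0.865/225) = 0.03222
- SE under the alternative = √((0.18 × 0.82 + 0.09 × 0.91)/225) = 0.03194
- Power = Φ((0.09 − 1.960 × 0.03222)/0.03194) = Φ(0.841) = 80.0%

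The same formula one-sided gives 87.7%. The stated figure therefore fits a two-sided uncorrected chi-square.

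**Chi-square against Fisher.** All 226 × 226 outcome tables were enumerated (two-sided 0.05):

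| | Chi-square, uncorrected | Fisher |
|---|---|---|
| Power, 18% vs 9% | 80.9% | 76.9% |
| Size at common rate 9% | 5.0% | 3.4% |
| Size at 13.5% | 5.1% | 3.7% |
| Size at 18% | 5.0% | 3.8% |

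Under the design assumptions, 4.0% of trials are significant by chi-square and not by Fisher. The reverse never occurs. For example, with 20 QuitGuide abstainers, significance needs 34 Smart-T abstainers by chi-square and 35 by Fisher. Fisher would need about 244 per arm for 80% power (79.99% at 242, 80.4% at 244). Sparse cells give no reason to choose it: 225 × 0.18 = 40.5 and 225 × 0.09 = 20.25 abstainers are expected.

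**Effect of the strata.** This was simulated: 450 participants, 20,000 runs per setting. Race and sex shares come from section F. Assumed, because the documents give none: a 50/50 split on cigarettes per day, permuted blocks of 2, and one common odds ratio for quitting per factor (race as White vs other). Race was taken at 2 or 4 levels. Marginal rates were 18% vs 9% for power and 13.5% in both arms for size.

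| Assumed odds ratio per factor | Power, CMH minus chi-square (points) |
|---|---|
| 1.0 | −0.2 |
| 1.5 | +0.1 to +0.2 |
| 2.0 | +0.9 |
| 2.5 | about +1.6 to +1.8 |
| 3.0 | +2.2 to +2.4 |

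Chi-square size falls from 4.9–5.3% at odds ratio 1.0 to 3.9–4.2% at 3.0. The uncorrected Cochran-Mantel-Haenszel (CMH) test stays at 4.8–5.2%, with power of about 80 to 84%. With a continuity correction the CMH loses what it gains (power 76.3–80.7%, size 3.4–3.7%). A logistic likelihood-ratio test behaves much like the uncorrected CMH (gain 0.2–2.9 points, size 5.1–5.4%). The Mantel-Haenszel risk-difference interval covers 94.7–95.2%; its mean width is 12.5 points at odds ratio 1.0 and 11.9 at 3.0, against 12.5 unadjusted.

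A second simulation with different assumed effects and 16 strata agrees in direction. Chi-square against CMH power was 81.0% vs 80.7% with no stratum effects, 81.1% vs 81.5% with moderate effects and 81.5% vs 83.6% with strong effects.

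**Sparsity.** Other race: 450 × 0.06 = 27 people, 27 × 0.135 ≈ 3.6 abstainers. The smallest of 16 strata: 450 × 0.06 × 0.39 × 0.5 ≈ 5 people. With White vs all other, the smallest of 8 strata: 450 × 0.41 × 0.39 × 0.5 ≈ 36 people, about 5 abstainers.

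**The case against.** The strongest reply is that the planned test is valid and the default is clear. Sections E and F both refer to the chi-square analysis, and the stated 80% matches that test. The gain from stratifying is nil or slightly negative without prognostic strata. It reaches 0.9 points only if all three factors have an odds ratio of 2.0 together, a 2 × 2 × 2 = 8-fold range of odds between extreme strata (27-fold at 3.0). On this view it is enough to name the chi-square and add cigarettes per day to the regression. Most of this stands: it sets the size of the point, and that smaller change would cure the ambiguity. It would still leave the primary test out of line with the allocation, when aligning them costs only wording.

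A reader might infer three stronger things:

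- *The type I error is inflated by ignoring the strata.* It is not; the error is towards conservatism.
- *Leaving two tests open lets the analyst pick the favourable one at the expense of false positives.* Running both and keeping the better result is exactly the uncorrected chi-square, with size about 5%.
- *The 80% is wrong, or the one-directional hypothesis means a one-sided test.* The 80% reproduces for a two-sided test, and a directional hypothesis does not by itself make the test one-sided.

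**Conclusion.** The point holds as a modest one that is worth correcting. The primary test omits race, sex and cigarettes per day although allocation uses them. The cost lies between nothing material (CMH about 0.2 points lower) and about 2.4 points of power, with chi-square size down to about 3.9–4.2% at the top of the assumed range. Those figures depend on assumed stratum effects, an assumed cigarettes-per-day split and an assumed block size.

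The comparison of the two permitted tests needs only the plan's own rates and sample size: 80.9% exact power for chi-square and 76.9% for Fisher, about 3 points below the stated 80%. That shortfall arises only if Fisher is chosen, which the text does not favour.

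The staff calls are a separate, smaller matter. They follow randomisation and are triggered by low EMA completion, while missed iCO tests count as smoking, so they are tied to the outcome. Adjusting a treatment-effect model for them could bias its estimate. The plan only permits this and does not attach it to Aim 1.

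**What to change.** In section E, Aim 1:

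1. Name one primary test: a two-sided CMH test at 0.05 without continuity correction, stratified by race, sex and cigarettes per day at the levels used in the randomisation. A logistic model for treatment adjusted for the same three factors is an acceptable alternative.
2. Set a rule for sparse race levels before outcomes are viewed by arm. One option is White vs all other if any level has fewer than 40 participants in both arms combined (40 × 0.135 ≈ 5 abstainers). The cut-off is a convention, not a figure from the documents. On the expected shares, the 27 people of other race would trigger it if race has four levels.
3. Report the Mantel-Haenszel difference in abstinence proportions with its 95% CI. The effect measure stays a comparison of proportions.
4. Delete the Fisher option and keep the uncorrected chi-square as supportive.
5. State that the 80% was computed for the two-sided uncorrected chi-square (the sponsor should confirm this), and that the stratified test has about the same or slightly higher power, about 80 to 84% under assumed stratum effects. The power statement then does not appear to describe a test that is no longer primary.

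In section D, exclude staff calls as a covariate in treatment-effect models and report them by arm.

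The cost is wording only. The stratification factors are known for every randomised participant, and no extra participants, data or procedures are needed.

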Perceived Neighborhood Disorder and decay	15		X		Sleep
Collective Efficacy	10		X		Smoking Items
Informal Integration with Neighbors	3		X		Pandemic Stress Index
Fear & Mistrust	7		X		Covid Vaccine
Personal Victimization	3		X		
Perceptions of Mobile Phone Intervention Questionnaire	23		X		
Covid Vaccine	5		X	X	
Delay Discounting Task (TOAD)	10		X		
Time needed to complete assessment (minutes)	--	8	60	40	†Note: Daily Diary EMAs also contain all Random EMA items
Note. *Event EMA's only. Screen = Screening; Base = Baseline; 26-W = 26Week Post-Quit Follow-Up.					

participant's pre-set bedtime. If the participant does not respond to the daily diary assessments, they will be rescheduled (up to 2 times) 15 minutes later. A carbon monoxide test will be included as one component of this EMA 3 days each week. Participants will not receive credit for completing the end of day EMA if they do not complete the prompted iCO breath tests. Both the morning and end of day daily diary EMAs will include all random sampling items. Constructs that will be assessed are listed in Table 3 and actual EMA items are presented in the Appendix. Note: During one EMA each week, participants will be asked multiple questions about the usefulness of their app (see Appendix).

*Random sampling.* Participants will be prompted to complete random EMAs, scheduled to occur during each participant's normal waking hours, 3 times each day for 5 weeks (1 week pre-cessation and 4 weeks post-cessation) and 1 time per day for the next 9 weeks (week 6 through 14). Random sampling will not be conducted during weeks 15-27. EMA items will assess the 6 items used for the lapse risk estimator (i.e., urge to smoke, stress, recent alcohol use, interaction with other smokers, cessation motivation, and cigarette availability). Other relevant constructs will also be assessed during random sampling (e.g., recency of smoking, odds of smoking today; See Table 3 and Appendix).

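### Does leaving open how many missed breath tests count as failure make the week-26 abstinence outcome unusable as planned?

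*Combined protocol and SAP*

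**What the plan says.** Section E, Aim 1, counts a participant as abstinent at 26 weeks after the quit date when both the iCO breath test and self-report show no smoking over the preceding 7 days. The arms are compared by chi-square or Fisher's exact test. The intention-to-treat rule is one "wherein participants who miss iCO EMAs will be considered not abstinent". On missing data the plan says "If the combined missing rate is very small, say less than 5%, then we may safely perform the data analysis on the available data", or else on the intention-to-treat data. If the missing rate is high, sequential multiple imputation is explored and compared with both of those analyses.

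The daily-diary text under Description of Study Measures gives the schedule: "A carbon monoxide test will be included as one component of this EMA 3 days each week". Biochemical Assessment of Smoking Status agrees ("the Bedfont iCO smokerlyzer will be used to verify smoking status on 3 days per week"), sets the cutoff at 6 ppm or below, and adds: "Smoking abstinence will be measured daily via EMA self-reports". For planning, Section E states: "Assuming an 80% iCO compliance rate for each participant, we anticipate 62 iCO measures per participant over the study". On power it says "we have 80% power to detect a 9% difference in biochemically confirmed 7-day point prevalence abstinence at 6 months", for 18% against 9% with 225 per group.

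No section says how many of the three tests in the window must be missed before the rule applies.

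**The concern.** The rule belongs to the primary outcome, and the plan itself expects one test in five to be missed. If a single miss were enough, many genuine quitters would be scored as smokers, and the outcome would partly measure test completion. Two analysts could obtain different primary results from the same data. The missing rate that is compared with 5% depends on the same count, so an open definition feeds an open choice of analysis. The count could also be settled after the missing patterns have been examined.

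**Working it through.** **Inputs from the documents.** 225 per arm, 18% against 9%, alpha 0.05 (taken as two-sided), 3 tests per week, 80% compliance.

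**Assumptions.** The 80% is a whole-study figure; here it is applied to abstainers at week 26 and to both arms. The documents give no within-person correlation of misses (rho), so it is varied from 0 to 1.

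**The plan's figures.**
- Power, pooled variance: mean rate 0.135; null standard error √(2 × 0.135 × 0.865/225) = 0.0322; alternative standard error √((0.18 × 0.82 + 0.09 × 0.91)/225) = 0.0319. Then Φ((0.09 − 1.96 × 0.0322)/0.0319) = 0.80. The stated 80% reproduces; Fisher's exact test gives 0.77.
- Expected tests: 26 × 3 × 0.80 = 62.4, matching the stated 62.

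**The window.** One pre-quit week plus 26 post-quit weeks makes 27 study weeks, and tests run through week 27. The 7 days ending 26 weeks after the quit date are therefore study week 27, with three scheduled tests. Only the count is open.

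**Share of true abstainers scored as smokers.**
- Independent misses: any miss, 1 − 0.8³ = 48.8%; two or more missed, 3 × 0.2² × 0.8 + 0.2³ = 10.4%; all three missed, 0.2³ = 0.8%.
- rho = 0.5, beta-binomial with a = 0.8 and b = 0.2: P(all three done) = 0.8 × 1.8 × 2.8/6 = 0.672; P(exactly two) = 3 × 0.8 × 1.8 × 0.2/6 = 0.144; P(none) = 0.2 × 1.2 × 2.2/6 = 0.088.
- rho = 1: 20% under every rule.

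| Rule for verification | rho 0 | rho 0.5 | rho 1 |
|---|---|---|---|
| All three tests | 48.8% | 32.8% | 20% |
| At least two | 10.4% | 18.4% | 20% |
| At least one | 0.8% | 8.8% | 20% |

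At 95% compliance the all-three loss falls to 14% (rho 0) or 9% (rho 0.5).

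**Effect on the comparison.** With equal completion, both rates are multiplied by the same retained share. Under the strictest rule with independent misses, 18% and 9% become 0.18 × 0.512 = 9.2% and 0.09 × 0.512 = 4.6%. The ratio stays at 2, and equal true rates stay equal.

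**Effect on power, only if 18% and 9% are rates before missed tests count as smoking.** All three: 49% (rho 0) or 61% (rho 0.5). At least two: 75% or 70%. At least one: 80% or 76%. All-or-none misses: 69% under any rule. If the rates already include missed tests: 80%.

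**The 5% line.** At 80% compliance, only the at-least-one rule can give a missing rate below 5%, and only when rho is below about 0.3 (at rho 0.3 the rate is 5.0%). There the choice of analysis matters little. If 18% and 9% are the missing-as-smoking rates, dropping 5% of each denominator gives 18/0.95 = 18.9% and 9/0.95 = 9.5%.

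**The case for a change.** The strongest opposing case is differential completion. Each Smart-T assessment ends with a treatment message, whereas in the QuitGuide arm the assessments are an add-on for the study. Completion could differ by arm in either direction, and a strict count would turn that into an apparent difference in abstinence. The imputed and available-data analyses also need a definition of a missing outcome, so they do not settle the count by themselves. The plan does not say that missing patterns will be examined without sight of the arms.

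Much of this stands: the count is unstated, and a strict rule is the more exposed to unequal completion. But the documents give no completion figure by arm, so this is a possibility without a size. The wording does not literally say that a single miss fails a person; it speaks of participants and tests in the plural. The rationale in Biochemical Assessment of Smoking Status, self-report combined with CO levels suggesting recent abstinence, fits spot verification at least as well. Looser counts have a cost too: "The half-life of CO is up to 8 hours depending on a variety of factors", so one clean test says little about days without a test. No count is plainly right.

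**Conclusion.** The omission is genuine, but it is a detail that analysts can fill sensibly, and no change to the plan follows. The cutoff, the schedule, the 7-day window and the treatment of missing as smoking are all given; the minimum number of completed tests is not. At 80% compliance the share of abstainers lost is 20% to 49% if any miss counts and 0.8% to 20% if one completed test suffices. These are conditional scenarios. They rest on a whole-study compliance figure carried to week 26 and on assumed within-person correlation.

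The damaging figures need the strictest reading. The loss of power also needs 18% and 9% to be rates before missed tests are counted. The plan states its power for biochemically confirmed abstinence, so the other reading is plausible, and under it 80% stands. With equal completion no count biases the comparison. If missingness is high, the imputed and available-data results are set beside the intention-to-treat result, so one reading of that rule would not be the only evidence. What remains is a choice between strict verification and retaining true quitters, on which competent analysts may differ.
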